6.4 Dose Rationale

The patients will continue on the dose and schedule given in the relevant base trial. Reduced dose can be administered in accordance with the mitigation strategies (Section 9.4 to 9.5.6) or at the discretion of the treating physician based on individual patient observed toxicity profile and after consultation and agreement by the Genmab Medical Officer.

7. TRIAL OBJECTIVES AND ENDPOINTS

Objectives	Endpoints
Primary 
The primary objective of the trial is to collect long-term safety data from patients with solid tumors who have been treated with tisotumab vedotin and completed any base trial (i.e., GEN701 or GEN702)	
Adverse events
Secondary 
To further evaluate the anti-tumor activity of tisotumab vedotin	
Objective response rate assessed by tumor shrinkage (according to the Response Evaluation Criteria In Solid Tumors version 1.1 [RECIST 1.1]) including change in prostate specific antigen (PSA) for patients with prostate cancer and CA 125 for patients with ovarian cancer

8. INVESTIGATIONAL PLAN

8.1 Overall Trial Design and Plan

This is an open-label, multicenter trial to collect long-term safety and efficacy data and to provide ongoing access to tisotumab vedotin for patients with solid tumors who have completed a tisotumab vedotin base trial. Patients demonstrating clinical benefit but who have been withdrawn from the base tisotumab vedotin trials for reasons that are not considered critical and unmanageable for the safety of the patient (as evaluated by the investigator and the sponsor) can also enter this protocol. For patients who received tisotumab vedotin as a single-agent in the base trial, tisotumab vedotin will be given according to the dosing level and schedule administered in the base trial at the time of exiting. Reduced dose can be administered in accordance with the mitigation strategies (Section 9.4 to 9.5.6) or at the discretion of the treating physician based on individual patient observed toxicity profile and after consultation and agreement by the Genmab Medical Officer. Patients will be treated with the tisotumab vedotin dosing regimen followed by the patient in the base trial, until the investigator determines that the patient is no longer benefitting from treatment (i.e., disease progression or unacceptable toxicity has occurred), the trial is terminated by the sponsor, the patient withdraws consent, or for other reasons as defined in this protocol.

In the Treatment Phase, investigators will monitor and assess the patients for response to treatment and for disease progression. Timing and assessments are outlined in the Schedule of Activities (Table 1). Any SAEs, non-serious grade ≥ 2 ocular AEs, non-serious grade ≥ 3 AEs, overdose and/or medication errors, and pregnancies should be reported to the Safety CRO by trial site personnel within 24 hours of their knowledge of the event. All (S)AEs should be reported from the time the patient has signed the ICF until the End-of-Trial (EOT) Visit, or until the patient withdraws consent or starts subsequent anti-cancer therapy, whichever occurs first.

An EOT Visit will occur 30 days after the last administration of trial drug. However, if a patient is unable to return to the site at that time or if the patient is scheduled to start subsequent treatment, this visit should be performed as soon as possible after the last administration of trial drug.

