8.2 Schedule of Activities

Table 1: Trial Flow Chart - 1Q3W Treatment Scheme

Procedure	Screening (up to 21 days before Day 1)	Treatment Period Cycle 1 – X (21-day cycle \pm 7 days) Day 1	End-of-Trial Visit (30 days after last dose + 1 week)	Comments
Informed consent	X			
Eligibility criteria	X			
Demography	X			
Height	X			
Weight	X	X		To be taken at screening and at start of each treatment cycle
Pregnancy test	X	X		To be taken at screening and at start of each treatment cycle for women of childbearing potential
Vital signs	X	X		Blood pressure pulse, heart rate and temperature taken at screening and before and after treatment
ECG	X	X		To be taken at screening and before each treatment
ECOG performance status	X			
Neuropathy assessment	X			
Skin assessment	X			
Ophthalmology evaluation	X	X	X	To be performed according to the schedule in the base protocol. Patients experiencing ocular symptoms must be referred to an ophthalmologist for prompt review (preferably within 72 hours and no later than within 1 week).
Laboratory sampling	X	X	X	Local laboratories will be used. Screening laboratory samples do not need to be repeated if performed at the base trial. Details on laboratory samples are provided in Section 10.3.4.

Procedure	Screening (up to 21 days before Day 1)	Treatment Period Cycle 1 – X (21-day cycle \pm 7 days) Day 1	End-of-Trial Visit (30 days after last dose + 1 week)	Comments
Trial drug administration		X		Treatment administration schedule to follow the treatment schedule in the base protocol.
Preventive eye therapy		X		Preventive eye therapy to be administered in relation to infusions as detailed in Section 9.5.4.
Response assessment (CT-scan, PSA, CA 125)	X	X	X	Last CT-scan of base trial to be used at screening if less than 4 weeks old, otherwise a new CT-scan needs to be obtained. Then, to be performed every 6 weeks (at the end of every second cycle) during Treatment Period, and response to be confirmed 4 weeks later. Response assessments will be recorded in the eCRF. PSA will be performed for CRPC patients. CA 125 will be performed for patients with ovarian cancer.
Radionuclide bone scan		X		For patients with CRPC, assessment of bone metastases by radionuclide bone scan every 12 weeks is recommended, but frequency should be based on local standards. If there is suspicion of progression, another bone scan will be performed twelve weeks later.
AE/SAE review	X	X	X	
Concomitant medication	X	X	X	

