8.5.3.2 Discontinuation from the Trial

The sponsor will make every effort to ensure patients are followed up for completion of safety assessment in the trial. Patients will be withdrawn from the trial for the following reasons:

- Trial medication is withdrawn
- Withdrawal of consent
- Lost to follow-up
- Death
- Sponsor terminates the trial

If a patient withdraws from the trial, an EOT Visit should be performed, preferably 30 days after last treatment.

When a patient withdraws consent for trial participation before completing the trial, the reason for withdrawal is to be documented in the electronic case report form (eCRF) and in the source document.

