11.2 Adverse Event Reporting

The investigator must report all directly observed AEs and all AEs reported by the patient. A general type of question should be used similar to “Do you have any health problems?” or “Have you had any health problems since your last visit?”

All AEs must be reported from the time the patient signs the ICF until 30 days after the last dose of tisotumab vedotin, or until the patient withdraws consent or starts subsequent anti-cancer therapy, whichever occurs first.

Any AE (signs, symptoms and diagnosis) occurring prior to signing the ICF must be recorded in the applicable base protocol eCRF.

Registration of Adverse Events in the eCRF:

- All AEs must be recorded in the eCRF.
- Grade 3 and 4 abnormal laboratory test results must be reported as AEs when these are assessed as clinically significant by the reporting investigator.

Reporting of Adverse Events to the Safety CRO:

- All SAEs
- Ocular grade ≥ 2 AEs
- All non-serious grade ≥ 3 AEs
- All events of overdose and/or medication errors, independent of intensity, must be reported as AEs to the Safety CRO.
- Any event of pregnancy must be reported as an AE to the Safety CRO.

Please refer to Section 11.5 for an overview of AE reporting timelines.

All deaths (including deaths due to disease progression) should be reported as an SAE.

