11.7 Follow-up on Adverse Events

All AEs should be followed until they are resolved or until 30 days after the last dose of tisotumab vedotin, until the patient withdraws consent or starts subsequent anti-cancer therapy, whichever occurs first. Serious adverse events, related non-serious grade ≥ 2 ocular AEs and non-serious grade ≥ 3 AEs that are ongoing after trial participation should be followed on a regular basis, according to the investigator's clinical judgment, until the event has been resolved or until the investigator assesses it as chronic and all queries have been resolved.

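### The fallback End-of-Trial Visit is tied to the last dose, not to the start of new therapy, so the closing safety checks can fall earlier than they need to

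*Protocol*

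**What the plan says.** Protocol Section 8.1 gives the standard rule: "An EOT Visit will occur 30 days after the last administration of trial drug". It then makes an exception for a patient who cannot return at that time, and also states: "if the patient is scheduled to start subsequent treatment, this visit should be performed as soon as possible after the last administration of trial drug". The synopsis has the same exception: "this visit should be performed as soon as possible after the last administration of trial drug". Neither text gives an earliest day or mentions the date on which the new treatment begins.

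The schedule in Section 8.2 (Table 1) heads the column "End-of-Trial Visit (30 days after last dose + 1 week", with an allowance on the late side only. Its entries are the ophthalmology evaluation, laboratory sampling, response assessment, AE/SAE review and concomitant medication. There is no later column. Section 8.5.3.2 says that on withdrawal "an EOT Visit should be performed, preferably 30 days after last treatment".

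The end of AE reporting is given in two ways. Section 8.1 says "All (S)AEs should be reported from the time the patient has signed the ICF until the End-of-Trial (EOT) Visit", or until consent withdrawal or new anti-cancer therapy if either is earlier. Section 11.2 requires reporting "until 30 days after the last dose of tisotumab vedotin, or until the patient withdraws consent or starts subsequent anti-cancer therapy", whichever comes first, with no cut-off at the visit. Section 11.7 follows the second pattern: "All AEs should be followed until they are resolved or until 30 days after the last dose of tisotumab vedotin", with the same two earlier stops.

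**The concern.** The primary objective is long-term safety and the primary endpoint is adverse events. Sections 11.2 and 11.7 treat the whole time up to day 30 or new therapy as valid follow-up of the last infusion. A closing visit serves that purpose best near the end of the period. The fallback instead pulls it towards the start.

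The exception also has no condition on when the new therapy begins. Read literally, it covers a patient whose next treatment starts after day 30 and who could attend on day 30 as usual.

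At stake is the completeness of post-dose safety data in a selected group: patients moving to another treatment and those who cannot attend at day 30. After the fallback visit, Table 1 schedules no further eye examination, laboratory draw or AE questioning. Under Section 8.1, AE reporting closes at that visit too.

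**Working it through.** No sample size, power or error rate bears on this point, and the plan gives no figure to reproduce. The check is day arithmetic.

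**Inputs from the protocol.** The safety period ends at day 30 after the last dose or at new therapy, whichever is first (Sections 11.2 and 11.7). The cycle is 21 days (Section 9.2). The standard EOT window is day 30 to day 37 (Table 1: 30 + 7).

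**Assumed inputs.** V is the day of the EOT Visit and S the day new therapy starts, both counted from the last dose. The documents give neither for the fallback, so a range is shown.

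**Formula.** Days of the safety period left after the closing visit = min(S, 30) − V.

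| Visit day V | S = 14 | S = 21 | S = 28 | S = 30 |
|---|---|---|---|---|
| 1 (most literal reading) | 14 − 1 = 13 | 21 − 1 = 20 | 28 − 1 = 27 | 30 − 1 = 29 |
| 7 (early mid-cycle stop) | 14 − 7 = 7 | 21 − 7 = 14 | 28 − 7 = 21 | 30 − 7 = 23 |
| 21 (stop decided at next planned dosing visit) | not applicable | not applicable | 28 − 21 = 7 | 30 − 21 = 9 |

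The last row is the most plausible setting. The exception presupposes a decision to stop. With 21-day cycles and scans recommended at the end of every second cycle, many such decisions will come around the next planned dosing day. The loss is then 7 to 9 days of the nominal 30 (7/30 = 23%; 9/30 = 30%).

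**After the fix.** With V = S − 1 and S no later than day 30, the remainder is S − (S − 1) = 1 day. In the plausible setting this recovers 7 − 1 = 6 to 9 − 1 = 8 days. If S is after day 30, the visit can stay at day 30 and nothing is lost.

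**What the lost days mean.** Under Section 8.1 they are days without AE reporting. Under Section 11.2 reporting stays open, but no visit is scheduled to ask about or examine for events. The two rules can also part in the other direction: a visit on day 37 would extend reporting under Section 8.1 by 7 days beyond the Section 11.2 limit.

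**The case against.** The strongest case against is that much of the AE information survives an early visit. Section 11.2 keeps reporting open to day 30 or new therapy. Section 11.7 follows ongoing serious events, and related ocular events of grade 2 or higher and events of grade 3 or higher, beyond participation. Section 11.4 asks for suspected drug-related events of these kinds at any later time. Patients with eye symptoms during the trial are referred whatever the visit schedule (Section 10.1.7). Laboratory values enter the eCRF only when clinically significant (Section 10.3.4). All endpoints are only listed, for about 25 expected patients. The SAP listings carry the last dose date and flag AEs after it, so a short observation period is visible. An early visit also guards against missing the visit altogether, or holding it after new therapy has begun.

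Most of this stands, and it limits the size of the point. It does not remove it. These provisions keep a channel for reporting but schedule no later examination, blood draw or AE enquiry, Section 11.4 is confined to suspected drug-related events, and Section 8.1 still closes reporting at the visit.

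Stronger readings are tempting but unsupported:

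- A reader might infer that most of the post-dose period is routinely lost. That needs a stop in the first days of a cycle, and the documents give no frequency for it.
- A reader might infer that the fallback contradicts Section 8.5.3.2. Its wording states a preference and so allows an earlier visit. Table 1 only lacks an early side that would reflect the express exception in Section 8.1.
- A reader might infer a general loss of tumor data. Section 10.2 ends efficacy scans at progression, so the effect is mainly on patients who change therapy without progression.
- A reader might infer that this is the only contact after the last dose. When treatment stops at a planned dosing visit or end-of-cycle scan, that contact also follows the last dose.

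**Conclusion.** The point holds as a modest, cheaply corrected weakness. As written, the fallback ties the visit to the last dose with no earliest day, while the protocol's own safety period runs to day 30 or new therapy. The closing eye, laboratory and AE review can therefore come sooner than needed, and under Section 8.1 AE reporting stops with it.

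The likely size is about 7 to 9 of 30 days for an affected patient. This assumes a decision to stop at about day 21 and new therapy on day 28 to 30. The number of affected patients cannot be derived from the documents. Some shortening below 30 days is unavoidable whenever new therapy starts early. The aim of a visit as late as feasible before new therapy is a reviewer's standard: it follows from the period in Sections 11.2 and 11.7 but is not stated in the documents. No hypothesis test or estimate is at risk; the effect is on the completeness of the primary safety listings.

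**What to change.** 1. In Section 8.1 and the synopsis, state that the EOT Visit takes place as close as possible to 30 days after the last dose and, if subsequent anti-cancer therapy is planned, before its first administration and as near to it as feasible.
2. Give the EOT column of Table 1 the matching early window, or a footnote pointing to the exception.
3. Reconcile the end of AE reporting in Section 8.1 and the synopsis with Section 11.2, so that the date of the visit does not by itself decide when collection stops.

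The change is a few sentences and one table header. It adds no visit and alters only the timing of assessments, not treatment or the start of the next therapy. The cost is tighter scheduling for sites and a small risk that the visit is missed, or overtaken if new therapy is brought forward.

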8.2 Schedule of Activities

Table 1: Trial Flow Chart - 1Q3W Treatment Scheme

Procedure	Screening (up to 21 days before Day 1)	Treatment Period Cycle 1 – X (21-day cycle \pm 7 days) Day 1	End-of-Trial Visit (30 days after last dose + 1 week)	Comments
Informed consent	X			
Eligibility criteria	X			
Demography	X			
Height	X			
Weight	X	X		To be taken at screening and at start of each treatment cycle
Pregnancy test	X	X		To be taken at screening and at start of each treatment cycle for women of childbearing potential
Vital signs	X	X		Blood pressure pulse, heart rate and temperature taken at screening and before and after treatment
ECG	X	X		To be taken at screening and before each treatment
ECOG performance status	X			
Neuropathy assessment	X			
Skin assessment	X			
Ophthalmology evaluation	X	X	X	To be performed according to the schedule in the base protocol. Patients experiencing ocular symptoms must be referred to an ophthalmologist for prompt review (preferably within 72 hours and no later than within 1 week).
Laboratory sampling	X	X	X	Local laboratories will be used. Screening laboratory samples do not need to be repeated if performed at the base trial. Details on laboratory samples are provided in Section 10.3.4.

Procedure	Screening (up to 21 days before Day 1)	Treatment Period Cycle 1 – X (21-day cycle \pm 7 days) Day 1	End-of-Trial Visit (30 days after last dose + 1 week)	Comments
Trial drug administration		X		Treatment administration schedule to follow the treatment schedule in the base protocol.
Preventive eye therapy		X		Preventive eye therapy to be administered in relation to infusions as detailed in Section 9.5.4.
Response assessment (CT-scan, PSA, CA 125)	X	X	X	Last CT-scan of base trial to be used at screening if less than 4 weeks old, otherwise a new CT-scan needs to be obtained. Then, to be performed every 6 weeks (at the end of every second cycle) during Treatment Period, and response to be confirmed 4 weeks later. Response assessments will be recorded in the eCRF. PSA will be performed for CRPC patients. CA 125 will be performed for patients with ovarian cancer.
Radionuclide bone scan		X		For patients with CRPC, assessment of bone metastases by radionuclide bone scan every 12 weeks is recommended, but frequency should be based on local standards. If there is suspicion of progression, another bone scan will be performed twelve weeks later.
AE/SAE review	X	X	X	
Concomitant medication	X	X	X	

IQ3W=once every 3 weeks; AE=adverse event; CT=computerized tomography; CRPC=castration-resistant prostate cancer; ECG=electrocardiogram; ECOG=Eastern Cooperative Oncology Group; eCRF=electronic case report form; PSA=prostate specific antigen; SAE=serious adverse event

8.3 End of Trial Definition

The trial is considered completed when tisotumab vedotin has been granted Marketing Authorization in the specific country and the last patient has been transferred to an approved treatment or sponsor stops the development of tisotumab vedotin.

8.4 Number of Patients

Any patient who has completed the treatment period of one of the base tisotumab vedotin trials (e.g., GEN701, GEN702) and has shown a clinical benefit of stable disease (SD) or better, or not completed treatment as defined in the base protocol for reasons that are not considered critical and unmanageable for the safety of the patient and the patient clearly showed response of partial response (PR) or better, and who wishes to continue treatment with tisotumab vedotin and fulfills the enrolment (inclusion and exclusion) criteria can participate in this trial. It is estimated that approximately 25 patients will enter the GCT1015-03 trial.

8.5 Trial Population

Eligibility in GCT1015-03 requires that patients must have completed the base trial and have not received any other anti-cancer treatment prior to inclusion in the current trial, and they must not have experienced radiographic disease progression or clinical signs of symptoms of instability requiring urgent intervention. Screening laboratory samples and computerized tomography (CT)-scan do not need to be repeated if these were performed as part of the base trial within the required timeframes (21 days and four weeks, respectively, before Cycle 1 Day 1 of the current trial). Prospective approval of protocol deviations to recruitment and enrolment criteria, also known as protocol waivers or exemptions, are not permitted.

The inclusion and exclusion criteria for enrolling patients in GCT1015-03 are described below. If there is a question about the inclusion or exclusion criteria below, the investigator should consult with the appropriate sponsor representative before enrolling a patient in the trial.

8.5.1 Inclusion Criteria

Patients **MUST** satisfy all of the following entry criteria before they will be allowed to participate in the trial:

1. Patients must have either:
 - a) completed the base trial and have shown a clinical benefit of SD or better and have never met any withdrawal criteria as defined in the tisotumab vedotin base protocol, or
 - b) not completed treatment as defined in the base protocol for reasons that are not considered critical and unmanageable for the safety of the patient (as evaluated by the investigator and/or the sponsor) and the patient clearly showed response of PR or better.

2. Patients must not have experienced radiographic disease progression or clinical signs of symptoms of instability requiring urgent intervention.
3. Patients must not have received any other anti-cancer treatment (including surgery, radiation or systemic chemotherapy) since the base trial.
4. Acceptable renal function defined as: Glomerular filtration rate (Cockcroft-Gault) > 45 mL/min.
5. Acceptable liver function defined as:
 - a) Alanine aminotransferase and aspartate aminotransferase ≤ 3 times the upper limit of normal (ULN); if liver tumor/metastases are present, then $\leq 5 \times$ ULN is allowed,
 - b) Bilirubin $\leq 1.5 \times$ ULN, except in patients diagnosed with Gilbert's syndrome, direct bilirubin $\leq 2 \times$ ULN.
6. Acceptable hematological status (hematologic support is allowed if administered at least one week before scheduled Cycle 1 Day 1) defined as:
 - a) Hemoglobin ≥ 5.6 mmol/L (~ 9 g/dL). An absolute value > 8 g/dL is allowed if stable (> 4 weeks) during the base trial.
 - b) Absolute neutrophil count $\geq 1500/\mu\text{L}$ ($1.5 \times 10^9/\text{L}$).
 - c) Platelet count $\geq 75 \times 10^9/\text{L}$.
7. Eastern Cooperative Oncology Group (ECOG) performance status of 0 or 1.
8. A negative serum pregnancy test (if female and aged between 18-55 years old).
9. Patients, both females and males, of reproductive potential must agree to use adequate contraception during and for six months after the last infusion of tisotumab vedotin.
 - a) Adequate contraception for women is defined as hormonal birth control or an intrauterine device (safe hormonal contraceptives include contraceptive pills, implants, transdermal patches, hormonal vaginal devices or injections with prolonged release). In countries where two highly effective methods of contraception are required this will be an inclusion criterion (refer to [Appendix 2](#)).
 - b) Male patients must be willing to use a latex condom during any sexual contact with females of childbearing potential during and for six months after the last infusion of tisotumab vedotin, even after having undergone a successful vasectomy.
 - c) In order to be considered as sterilized or infertile, a patient must have undergone surgical sterilization (vasectomy/bilateral tubectomy; hysterectomy and bilateral ovariectomy) or be postmenopausal (12 months or more with no period prior to enrolment).

10. Following receipt of verbal and written information about the trial, patients must provide signed informed consent before any trial-related activity is carried out.
11. Acceptable coagulation status as defined in the applicable base protocol:
 - GEN701: Acceptable coagulation status: international normalized ratio (INR) ≤ 1.2 (without anticoagulant therapy) and activated partial thromboplastin time (aPTT) ≤ 1.25 ULN; patients on stable doses of therapeutic anti-coagulative treatment for ≥ 8 weeks (e.g., warfarin) must have an INR ≤ 3 .
 - GEN702: Acceptable coagulation status defined as: INR ≤ 1.2 (without anticoagulant therapy) and aPTT \leq ULN.

